1. PURPOSE OF THE STUDY

a. Brief Summary

Adherence to prescription opioid and opioid tapering as indicated are critical for safe chronic opioid therapy for chronic pain, but this can be difficult for patients experiencing prescription opioid craving.

Because pain catastrophizing is proposed as a possible treatment target by our and others' preliminary results, the proposed study aims to determine whether pain catastrophizing is a treatment target to reduce prescription opioid craving and to investigate whether negative affect and stress hormones are potential mediators.

b. Objectives

We hope to learn whether a psychology intervention to lower pain catastrophizing will reduce opioid craving, and whether psychological and physical distress will be potential mediators of the treatment effect.

c. Rationale for Research in Humans

The purpose of this study is to examine the effect of a psychological intervention on opioid craving and medication misuse in patients taking prescription opioid for pain management.

2. STUDY PROCEDURES

a. Procedures

Potentially eligible patients will complete an online prescreening survey. Based on the responses to the online prescreening survey, potentially eligible patients will be contacted via phone for additional explanation about the study to the patient, the brief phone screening to ensure the eligibility, and scheduling a laboratory experiment visit. As recommended not to ask a sensitive question (I.e., suicidal thought) during the phone screening, we will inform participants over the phone that their eligibility can be fully determined only after the full consent in the laboratory and we will pay their travel (\$25

for those living within an 1-hour driving distance and \$50 for those living beyond it).

Potentially eligible patients will be invited for a laboratory experiment (Study 1, 1.5 hours). After obtaining a consent and determining the eligibility, participants will participate in the Study. We will utilize the suicide protocol if a participant is ineligible due to a suicidal ideation. Arm 1 study consists of two Studies; Study 1 will be a laboratory experiment and Study 2 will be a daily home practice. For Study 1, participants will be randomized to three conditions using previously validated protocols (Roditi et al., 2009, Taub et al., 2017): control, pain catastrophizing induction, and reduction. For Study 2, participants will be randomized again to two conditions: control and pain catastrophizing reduction.

During the Study 1 laboratory experiment, patients will undergo 1) vital sign checks (heart rate, blood pressure, body temperature), 2) blood draw(7 ml) and salivary sample collection, 3) a pain catastrophizing protocol with a cold pressor testing, and 4) FOUR salivary sample collections (immediately after pain catastrophizing protocol, 10 min, 20 min, & 30 min after the cold pressor test). Patients' physiological states will be continuously monitored such as Heart Rate, Skin Conductance, skin temperature, Respiration Rate, facial EMG, and blood pressure.

This study will use previously validated two pain catastrophizing protocols (Taub et al, 2017 and Roditi et al, 2009). Briefly, the induction procedures are; first, ask participants to think and write about their past pain flare up episode for 10 minutes and then, read 10 pain catastrophizing statements. Secondly, participants will read a pain catastrophizing statement of their choice out loud while putting their non-dominant hand in a cold water. The reduction procedures are; first, ask participants to think and write about their best pain management case for 10 minutes and then, read 10 pain coping statements. Secondly, participants will read a coping statement of their choice out loud while putting their non-dominant hand in a cold water.

After completing Study 1, the participants will receive instruction about Study 2, which includes daily home practice of coping statement for 7 days (delivered via REDcap system), completing a daily survey for 14 days (5 minutes, delivered via REDcap system), and donate salivary cortisol (at the time of waking up, 30-min after waking up, and 9pm) at Day 1, 7, and 14. The collected salivary cortisol will be mailed to the lab with a pre-stamped envelope and an ice pack.

If patients need to take certain medications (Steroid or Benzodiazepines) within 3 days of a saliva sample collection, saliva samples will not be collected.

Added study 3 (arm 3)-----

Due to the unexpected event of COVID-19 pandemic, the study 3 (arm 3, online only) was added to examine the effect of pain catastrophizing on prescription opioid craving. Participants enrolled in the study 1 and 2 will NOT be allowed to participate in the study 3. Different from study 1 and 2, participants in study 3 do not need to have a lab visit (all remote study tasks).

Study 1, 2, and 3 will use the same inclusion criteria, but exclusion criteria for study 3 will be different because study 3 will not do cold pressor testing on the non-dominant hand and will not collect blood and saliva samples. Therefore, we removed the following exclusion criteria in the study 1 and 2: needle phobia, skin condition on the non-dominant hand, daily use of cortisol or benzodiazepine. However, we added ineligibility criteria for inability to use heart rate monitoring device and app because Study 3 will collect resting heart rate daily. During the phone screening, we will ask all eligibility questions except one sensitive question (I.e., suicidal ideation). We will inform participants that we have one more eligibility question, which can be asked only after they sign the phone consenting.

After the phone screening, we will do a phone consenting. A research coordinator will send the consent document to a participant via the REDCap system, which is a HIPPA compliant database. When sending the consent link, we will not include any PHI in the subject line. Then, the research coordinator will go over the consent over the phone and answer any questions. Participants will have a plenty of time to read the consent and can indicate whether they agree to participate or not on their own at home. Participants type their name and date if they agree to participate. After signing their consent, participants can download the consent and keep the copy for their own record. Once we obtain their consent, we will ask about suicidal ideation to determine their eligibility. Only the eligible participants will participate in Arm 3 study. We will use a suicide ideation protocol if a participant is ineligible due to suicide thought.

Participant in the study 3 will do the baseline survey and be randomized into two conditions: daily coping statement practice (50%) and no coping statement (50%). The participants in the daily coping condition will be asked to choose the coping statement of the day and rehearse throughout the day for the 15 days. Except this difference, participants in the both conditions will do a daily survey and check the resting HR for five minutes for the 15 days. The participant will receive a wrist heart rate device (i.e., a heart rate measuring device) before the baseline survey and heart rate will be anonymously collected. Also, participants in the both conditions will do a cognitive testing at day 1 (baseline), day 8, and day 15 (final study). Different from the study 1 and 2, study 3 will examine resting sympathetic cardiac levels and cognitive function as a mediator of the effect of the pain catastrophizing on craving.

Stanford is the only study site, University of Oklahoma will only conduct EDTA sample analysis

b. Procedure Risks

All members of the study team have been trained to conduct the research procedures in the safest manner possible. There are no known risks to complete the study procedures as all the procedures and questionnaires are validated in this patient population and this medical setting. However, patients may feel temporarily uncomfortable for blood draw, laboratory pain testing, and completing some questionnaires. To minimize the risk, we will exclude patients with a needle phobia and history of vasovagal syncope for blood draw. Additionally, vital signs will be assessed prior to the blood draw and throughout

the laboratory procedures. During the informed consent procedure, the patients will be informed that they can withdraw their consent anytime without penalty and their time will be compensated. Patient will have an option to not to answer any questions that make them feel uncomfortable. Finally, we will obtain the certificate of confidentiality to protect the privacy of research subjects by prohibiting disclosure of identifiable, sensitive research information to anyone not connected to the research except when the subject consents or in a few other specific situations.

c. Use of Deception in the Study

The exact study hypothesis and study procedures of part 1 are not completely described in the consent, but will be debriefed at the end of Experiment 1. **Use of Audio and Video Recordings**

No audio or video recording will occur. **Alternative Procedures or Courses of Treatment**

Participants are free to pursue the treatment of their choice at any time during and/or after the study.

f. Will it be possible to continue the more (most) appropriate therapy for the participant(s) after the conclusion of the study?

Participants are free to pursue the treatment of their choice at any time during and/or after the study

g. Study Endpoint(s)

Each participant will meet the study endpoint once he/she completes the daily survey for 14 days after Study 1 laboratory visit. The study will end once the target enrollment is reached.

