8. PARTICIPANT POPULATION

a. Planned Enrollment

- (i) 156 participants (50% female) will be recruited at the Stanford Systems Neuroscience and Pain Lab.
- (ii) All participants will be enrolled at Stanford. Patients with chronic pain and opioid medication use will be enrolled.

(iii) Patients, aged at least 18 years old, visiting our pain clinic for chronic pain treatment will be recruited because we want to identify a psychological treatment target for prescription opioid craving and misuse in patients with chronic pain conditions.

(iv) We will partner with the Research Participant Engagement Program (RPEP) team for Honest Broker outreach. Potential participants are identified via STARR and invited by RPEP team (honest broker) on behalf of study team. See Section 16 for Honest Broker study invitation letters. We will be using Postal Mail and Research Registry honest broker outreach. For Postal Mail, study team may support the process by sticking pre-printed address labels (created by RPEP, the honest broker) on the envelopes.

b. Age, Gender, and Ethnic Background

Participants, aged at least 18 years old of both genders and all racial and ethnic backgrounds will be included.

c. Vulnerable Populations

NA

d. Rationale for Exclusion of Certain Populations

The pain catastrophizing protocols (Taub et al, 2016, Roditi et al, 2009) have been validated only for adults with chronic pain. This study will be the first to use this protocol in patients taking opioid pain medications for chronic pain management. If this study finds no safety concerns in adult patients with chronic pain and chronic opioid therapy, a future study can include children.

e. Stanford Populations

Laboratory personnel, employees, and/or students will not be specifically recruited, although they will be able to participate if they visit our clinic.

f. Healthy Volunteers

NA

g. Recruitment Details

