9. RISKS

a. Potential Risks

i. Investigational devices

NA

ii. Investigational drugs

NA

iii. Commercially available drugs, biologics, reagents or chemicals

NA

iv. Procedures

Participants may experience discomfort from blood draw such as bleeding, soreness, bruising and stinging at the site of the blood draw. Participants may experience physical discomfort in undergoing cold water pressor test. To minimize the risk of physical discomfort, we will use our standard laboratory protocol (4 Celsius, 2 minutes), which is shown to induce "temporary" discomfort.

Online only Arm 3 study-----

No risk of physical discomfort in Arm 3 study

v. Radioisotopes/radiation-producing machines

NA

vi. Physical well-being

NA

vii. Psychological well-being

None of the questionnaires pose a risk to the participants. It is possible that subjects may feel uncomfortable answering some questions on the questionnaires; this risk will be minimized by allowing participants to refuse to answer a question. Additionally, some participants undergo pain catastrophizing induction protocol. We will use a validated pain catastrophizing protocol (IRB 11689, Taub et al., 2017, and Roditi et al., 2009), which is proven to "temporarily" induce catastrophic thinking about pain. For daily practice of pain coping statement, we will have only pain catastrophizing reduction and control condition. Finally, we will obtain certificate of confidentiality to protect the privacy of research subjects by prohibiting disclosure of identifiable, sensitive research information to anyone not connected to the research except when the subject consents or in a few other specific situations.

Arm 3 (online only) study-----

None of the questionnaires pose a risk to the participants. It is possible that subjects may feel uncomfortable answering some questions on the questionnaires; this risk will be minimized by allowing participants to refuse to answer a question. Also, we will collect the heart rate data anonymously and heart rate data will be recorded only with research email account and study id.

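### The Study 2 analysis does not say which Condition it means and has no Study 1 term; adding the Study 1 assignment and its interaction with Time is a cheap, minor improvement

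*Combined protocol and SAP*

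**What the plan says.** Section 2a allocates each in-person participant to control, induction or reduction for the laboratory session (Study 1). It then adds: "For Study 2, participants will be randomized again to two conditions: control and pain catastrophizing reduction". The same people continue: "After completing Study 1, the participants will receive instruction about Study 2".

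The two interventions overlap. In the Study 1 reduction condition participants "read 10 pain coping statements", and then "participants will read a coping statement of their choice out loud while putting their non-dominant hand in a cold water". Study 2 consists of "daily home practice of coping statement for 7 days" alongside daily surveys. Section 2g places the endpoint when a participant "completes the daily survey for 14 days after Study 1 laboratory visit". No washout is described.

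The Analysis Plan (at the end of Section 11) gives one model, a two-way Condition by Time repeated-measures ANOVA, for craving, cortisol and psychological distress. Mediation analyses follow only if Condition is significant. It does not tie Condition to a study, mention the other assignment, or say whether the second randomisation is stratified by the first. Section 8a gives the only sample size, "156 participants (50% female) will be recruited", without a split between Studies 1/2 and Study 3. Study 3 participants are separate people with a single assignment, so the point does not concern them.

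**The concern.** Each Study 1/2 participant carries two randomised assignments, and the model as written uses one. Shortly before Study 2, some of its controls will have rehearsed coping statements and others catastrophizing statements. If that still affects craving during the 14 days, the variation goes into the error term of the Study 2 comparison.

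Precision matters here because mediation, a stated objective in Section 1b, is run only after a significant Condition effect. Which test is meant also matters. A carry-over that stays constant over time enters the Condition main effect but cancels out of Condition by Time. A carry-over that fades over the 14 days enters Condition by Time, and a Study 1 main effect alone does not remove it. The interaction of Study 1 with Time is needed for that.

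**Working it through.** **Plan's own figure.** The 156 cannot be reproduced, because no power, effect size, SD or significance level is given.

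**Assumptions, not in the documents.** Two-sided 5% test; Study 1 allocated 1:1:1; Study 2 allocated 1:1 with n = 26, 39 or 78 per arm, so N = 2n (78 per arm puts all 156 in Studies 1/2). Induction and reduction shift craving by +s and -s residual SDs, so the gap between them is 2s.

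**Formulas.**
- Variance added when the term is omitted: v = 2s²/3.
- Variance factor from chance imbalance when the term is included and the second randomisation is unstratified: 1 + 2/(N - 4).
- Cost with no carry-over: sqrt(1 + 2/(N - 4)) - 1.
- Break-even: v = 2/(N - 4), so s = sqrt(3/(N - 4)). If only one Study 1 condition carries over, v = 2s²/9 and s = sqrt(9/(N - 4)).

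| Per arm | 2/(N - 4) | SE cost, no carry-over | Break-even s, both directions | Break-even s, one condition only |
|---|---|---|---|---|
| 26 | 2/48 = 0.042 | 2.1% | 0.25 | 0.43 |
| 39 | 2/74 = 0.027 | 1.3% | 0.20 | 0.35 |
| 78 | 2/152 = 0.013 | 0.7% | 0.14 | 0.24 |

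At s = 0.1, v = 0.0067. This is below break-even at every size, and the term raises the SE by 1.7%, 1.0% and 0.3%.

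**Bias.** With a true effect of -0.5 SD and an unstratified second randomisation, the simulated mean estimate was -0.50 with and without the term. A separate simulation covering simple, permuted and stratified allocation found bias of at most 0.008 SD, which is simulation noise.

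**Type I error.** Unstratified, the simulated rate for the Condition effect was 4.7% to 5.3% with or without the term. Stratified by Study 1 condition, the estimate does not vary with Study 1 imbalance, but the error term without the Study 1 factor still contains v. At s = 0.5 (a 1 SD gap), v = 2(0.25)/3 = 0.167, the effective cut-off is 1.96 × sqrt(1.167) = 2.117, and the two-sided rate is 3.4%. Simulations gave about 3.4% to 3.8%.

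**Condition main effect, upper case.** For a 0.5 SD Study 2 effect and a lasting s = 0.5 in both directions, noncentral t with d = 0.5/sqrt(1 + v) on N - 2 df, against d = 0.5/sqrt(1 + 2/(N - 4)) on N - 4 df, gives power without and with the term of 37% and 41% (n = 26), 52% and 58% (39), and 82% and 87% (78).

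**Condition main effect, fading carry-over.** If a 0.5 SD shift on Day 1 halves daily, the 14-day mean shift is about 0.5 × 2/14 = 0.07 SD. Under compound symmetry with within-person correlation 0.5 to 0.7, v is about 0.005 to 0.006, below break-even at all three sizes. The term then gives a small loss.

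**Condition by Time, fading carry-over.** For a linear slope over the 14 days, the same daily halving gives v of 0.18 to 0.30, well above break-even. In a two-time-point version (Day 1 to Day 14 change, residual variance 2(1 - correlation), s = 0.5 fading to zero, 0.5 SD difference in change), power without and with the terms is:
- correlation 0.5: 37% and 41%, 52% and 58%, 82% and 87%;
- correlation 0.7: 52% and 61%, 70% and 79%, 94% and 98%.

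If carry-over is constant, the change analysis gains nothing and pays the 0.7% to 2.1%.

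**Study 1 by Study 2 interaction.** The SE of a difference in Study 2 effect between two Study 1 conditions is sqrt(12/n). The difference detectable with 80% power is 2.8 × SE = 1.9, 1.6 or 1.1 SD. The 95% half-width is 1.96 × SE = 1.3, 1.1 or 0.8 SD.

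**The case against.** The strongest case against is that nothing in the documents shows material carry-over, and several passages suggest it is small. The exposure is 10 minutes of writing, some statements, and a cold-water test for which "we will use our standard laboratory protocol (4 Celsius, 2 minutes" sets the limit. Section 9a calls the induction effect temporary, although it says this of induction only. Section 2c plans a debriefing at the end of Experiment 1, and Section 9c has the experimenter check that physiological values are within normal limits before the session ends. If Day 1 follows the Study 2 instruction, its waking saliva sample implies at least one night in between. All of this stands as reason to expect little carry-over, though none of it measures craving afterwards. Leaving a prior randomised factor out of the model is also a defensible choice, and the firmer gap is that Condition is not defined by study.

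A reader might infer more than the documents support in three ways:
- That Study 1 contaminates or biases the Study 2 comparison. It does not, because participants are randomised again.
- That the test size is right whether or not the term is included. That holds only for an unstratified second randomisation, and the plan does not say which was used. The departure under stratification is towards conservatism.
- That the power differences at s = 0.5 are the expected loss. They are upper cases. For the main effect they need a 1 SD gap lasting two weeks after one visit.

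**Conclusion.** Minor: a cheap improvement, not an error. The two assignments and the missing term are plain in the documents, and the averaged Study 2 effect is unbiased with or without the term. Under unstratified allocation, omission costs precision only. Under stratified allocation it can also make the test conservative, at about 3.4% to 3.8% for a 1 SD gap.

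The likely benefit is modest. For the Condition main effect it needs a lasting shift of roughly 0.14 to 0.25 SD in both directions. For Condition by Time it depends on a sizeable Day 1 carry-over that then fades. All sizes rest on assumed arm sizes, allocation ratios and carry-over. The documents supply none of these, so confidence in a material gain is limited.

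**What to change.** State for each study which assignment Condition denotes, and state whether the second randomisation was stratified by Study 1 condition. In the Study 2 model, define Condition as the Study 2 assignment, add Study 1 condition and Study 1 condition by Time as fixed factors, and keep the Study 2 effect averaged over Study 1 conditions as the main estimate. Decide this before the Study 2 data are analysed, since the terms can help or slightly hurt and a later choice would be open to selection by result.

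A Study 1 by Study 2 interaction is optional. If reported, give confidence intervals and label it exploratory; it is too imprecise for a null result to show that the effect is consistent.

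The change needs no new data and does not alter trial conduct. The statistical price is the small SE increase tabulated above if allocation was unstratified and carry-over is nil. If allocation was stratified, it is two degrees of freedom in the between-subject test, with a matching loss per time contrast (for example 152 to 148 within-subject error df with three time points and 78 participants).

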h. Eligibility Criteria

i. Inclusion Criteria

For study 1, 2, and 3,

1. At least 18 years old
2. Chronic opioid therapy at least 3 months
3. Any chronic pain conditions at least 3 months

ii. Exclusion Criteria

For study 1 and 2,

1. Current diagnosis of cancer
2. Other severe psychiatric and cognitive conditions (schizophrenia, delusional disorder, psychotic disorder, dementia, Parkinson's or dissociative disorder)
3. An skin conditions on the non-dominant hand (pain testing site)
4. Non-English speaker
5. No access to email or smart phone
6. (For saliva collection) Daily use of cortisol or benzodiazepines
7. Being pregnant
8. Needle phobia for blood draw
9. Current suicide thoughts

added for study 3-----

For study 3,

1. Current diagnosis of cancer
2. Other severe psychiatric and cognitive conditions (schizophrenia, delusional disorder, psychotic disorder, dementia, Parkinson's or dissociative disorder)
3. Non-English speaker
4. No access to email or smart phone
5. Being pregnant
6. Current suicide thoughts
7. Concurrent psychological treatments during the 15-day study period.

i. **Screening Procedures**

New recruitment method will be used, the Research Participant Engagement Program (RPEP). RPEP will use coded diagnoses and procedures, clinical records, demographics with embedded identifiers, medications, names, telephone numbers, home address, date of birth, date of service, date of diagnosis, emails, and MRNs to recruit via postal mail.

Potentially eligible patients will complete an online prescreening survey. The online screening survey will assess patients' chronic pain and other health conditions, pain medication use, and prescription misuse, and craving. For prescription misuse and craving, the PROMIS item bank for the misuse of prescription pain medication and the COMM will be administered. This study will invite people endorsing chronic pain at least 3 months, taking opioid pain medications at least 3 months, and no craving or craving at any frequency on the PROMIS craving item (i.e., I experienced cravings for pain medication). Name, email, and phone number will be collected to invite eligible participants for the study.

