Participants will be okay to participate in other clinical trials except for clinical trials including pain self-management or psychological interventions. If a patient is interested in participating in other clinical trials including pain self-managements or psychological interventions, a patient will be informed of two options : the one will be participating in other studies after completing this study for 14 days and the other option will be not to participate in this study.

k. Payments to Participants

Participants will be compensated \$30 for Study 1, \$5 for daily survey for 14 days, \$5 for three at home saliva samples, and \$5 for completion of all study requirement. Therefore, when completing the whole study requirements, a participant receive a total of \$120.

Travel cost will be compensated: \$25 for people living within 60 miles and \$50 for people living beyond 60 miles.

Added for the Study 3, -----

For study 3, participants will be compensated \$25 for completing the baseline tasks (the 30 or 40-min survey, cognitive testing and blood pressure and HR measure), \$60 for completing the short-daily survey and blood pressure ($\$5 \times 12 \text{ days} = \60), and \$10 for completing a 10-min survey and HR measure at day 8, and \$20 for completing the final survey. When completing all the tasks, the participant will receive additional \$5. Therefore, the total compensation is up to \$120 ($=25+60+10+20+5$). Participants will receive check as compensation.

l. Costs to Participants

NA

m. Planned Duration of the Study

Participants will complete (i) the initial 2.5 hour-laboratory experiment (Study 1) and daily home practice of coping statement and daily survey (3-5 minutes, Study 2) for 14 days. (iii) This study estimates 3 years of data collection and 1 year of data analysis.

Added for study 3, -----

Participants will completed (i) the initial 45-60min baseline survey, cognitive testing, and resting blood pressure and HR measure, (ii) a brief daily survey, resting blood pressure and HR measure for 15 days and practicing a 5-min daily coping statement 15 days (only for the 50% of people who are assigned to the coping statement condition), (iii) a 10 min survey at Day 8 and blood pressure and HR measure, and (iv) 20 min-final survey and cognitive testing, and blood pressure and HR measure.

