11. PRIVACY AND CONFIDENTIALITY

All participant information and specimens are handled in compliance with the Health Insurance Portability and Accountability Act (HIPAA) and privacy policies of Stanford University, Stanford Health Care, and Stanford Children's Health.

Analysis Plan

We will conduct two-way repeated-measures ANOVAs (Condition \times Time) to test whether reductions in pain catastrophizing are associated with decreases in craving, cortisol levels, and psychological distress (depression and anxiety).

If a significant effect of Condition is observed, we will conduct mediation analyses to test whether the intervention's effects on craving are mediated by reductions in cortisol and psychological distress.

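### Study 2 names no craving baseline between the Study 1 manipulation and the start of home practice, so Condition × Time has no assured pre-practice reference

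*Combined protocol and SAP*

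**What the plan says.** Section 2a (Procedures) first randomises participants to control, induction or reduction of pain catastrophizing in the laboratory (Study 1). It then randomises them again to control or reduction for home practice (Study 2). On timing it says: "After completing Study 1, the participants will receive instruction about Study 2, which includes daily home practice of coping statement for 7 days", together with "completing a daily survey for 14 days (5 minutes, delivered via REDcap system") and saliva collected on waking, "30-min after waking up, and 9pm) at Day 1, 7, and 14". Section 2g confirms that the 14 survey days follow the laboratory visit. Nothing states which 7 of the 14 days carry practice.

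Section 8m (Planned Duration) describes the same period differently: "daily home practice of coping statement and daily survey (3-5 minutes, Study 2) for 14 days".

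The only craving measurement that the documents clearly place before Study 1 is the online prescreen in section 8i: "The online screening survey will assess patients' chronic pain and other health conditions, pain medication use, and prescription misuse, and craving". For misuse and craving, "the PROMIS item bank for the misuse of prescription pain medication and the COMM will be administered". The interval from prescreen to Study 2 is not given, and the prescreen is not named as an analysis baseline.

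Study 3 is handled differently: "Participant in the study 3 will do the baseline survey and be randomized into two conditions".

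The Analysis Plan (end of section 11) specifies two-way repeated-measures ANOVAs, Condition by Time, "to test whether reductions in pain catastrophizing are associated with decreases in craving", cortisol and distress. It makes mediation analysis conditional on a significant effect of Condition. It does not define the levels of Time or a baseline.

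**The concern.** A decrease needs a starting value. In Study 2 no survey is required to fall after the laboratory manipulation and before the first practice. If practice begins on Day 1 and acts the same day, the first level of Time is already treated. The two conditions would then differ by a constant amount across all 14 days, and a constant difference does not show in a Condition × Time interaction. A real effect could be reported as no change over time.

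A second loss applies however fast practice acts. Craving differs between people, and a pre-practice value on the same instrument would remove much of that variation from the comparison. The protocol already uses a pre-randomisation survey in Study 3, so the feature is familiar and feasible.

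**Working it through.** **Schedule.** Survey days minus practice days under section 2a: 14 − 7 = 7 survey days without practice.

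- Practice on Days 1–7: no practice-free lead-in, and 7 days of follow-up.
- Practice on Days 8–14: a 7-day pre-practice series. Section 2a does not exclude this, but nothing describes it.
- Section 8m (practice and survey both 14 days): no practice-free survey day.

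Whether a pre-practice survey exists therefore depends on a reading that the documents do not settle.

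**Inputs for the size.** There is no planned figure to reproduce: section 8a gives 156 participants, with no split by study, effect size, SD, alpha or power. I assumed n = 39 per arm, daily SD 1, equal correlation r between any two days, a two-sided t-test at 0.05, and a true effect of 0.6 SD present in full from Day 1.

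**Contrast against Day 1.** Mean of Days 2–14 minus Day 1: the true group difference is 0.6 − 0.6 = 0. The test rejects at its error rate, about 5% (4.9% in 4,000 simulated trials).

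**Same contrast against a pre-practice day.** Variance per person = (1 − r)(1 + 1/13). At r = 0.5 this is 0.5 × 14/13 = 0.538. SE = √(2 × 0.538/39) = 0.166; 0.6/0.166 = 3.61; power about 95%.

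**Condition comparison on the 14-day mean, no baseline.** Variance = (1 + 13r)/14. At r = 0.5 this is 7.5/14 = 0.536. SE = √(2 × 0.536/39) = 0.166; ratio 3.62; power about 95%.

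**Same comparison adjusted for one pre-practice survey.** Share of variance explained = r²/[(1 + 13r)/14]. At r = 0.5 this is 0.25/0.536 = 0.467. Remaining variance = 0.536 × 0.533 = 0.286. SE = √(2 × 0.286/39) = 0.121; ratio 4.96; power over 99%.

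| r | Variance explained by one survey | 14-day mean, no baseline | Change from pre-practice day | 14-day mean, adjusted |
|---|---|---|---|---|
| 0.3 | 26% | 99% | 85% | over 99% |
| 0.5 | 47% | 95% | 95% | over 99% |
| 0.7 | 68% | 87% | 99.6% | over 99% |

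**If the effect builds over a week (r = 0.5).** With Day 1 still untreated, Day 1 serves about as well as a separate pre-practice day (about 82% for each). If Day 1 already carries one-seventh of the effect, the mean effect over Days 2–14 is 0.6 × (27/7 + 7)/13 = 0.501. Against Day 1 the contrast is 0.501 − 0.086 = 0.415, ratio 2.50, power about 69%. Against a pre-practice day the ratio is 3.02, power about 85%.

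**The case against.** The strongest reply is that randomisation, not a baseline, makes the comparison valid. Study 2 has a concurrent randomised control, and the repeated-measures ANOVA also tests the Condition main effect, on which the plan makes mediation depend. A constant difference over the 14 days is what that test detects, with about 95% power above. This stands, and it rules out several stronger readings that a reader might infer.

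- **That the Study 2 effect cannot be measured, or that no model can repair the gap.** The between-condition effect is estimable without a baseline.
- **That a difference from Day 1 could not be told apart from chance imbalance.** The p-value of a randomised comparison already allows for chance imbalance.
- **That practice and surveys are known to start together.** Section 2a does not place the practice days. Section 8m points that way but conflicts with section 2a on duration.
- **That no craving was measured before practice.** The prescreen in section 8i did so. It may help as a covariate, but its interval is unstated and the daily craving instrument is not named, so it is not shown to be a usable first level of Time.
- **That any laboratory-day value must follow the manipulation.** Section 2a lists blood and saliva before it. A pre-manipulation survey is neither described nor excluded.

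Two further points are fair. A survey taken after the laboratory visit is still downstream of Study 1, so it is pre-practice but not untreated. The waking saliva sample on Day 1 may already precede practice, so the case for moving saliva is weak.

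**Conclusion.** The point holds as a gap in design and specification, not as a threat to validity. Study 2 has no designated craving baseline after Study 1 and before practice, its Time levels are undefined, and sections 2a and 8m disagree on how long practice lasts.

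The consequence depends on how fast practice acts. For an effect complete from Day 1, a contrast against Day 1 has only about 5% rejection. For one that builds after an untreated Day 1, little is lost on that contrast. The gain from adjustment does not depend on that timing: one survey explains 26% to 68% of the variance of the 14-day mean for r from 0.3 to 0.7. At r = 0.5 it lifts power from about 95% to over 99%. These figures rest on an assumed 39 per arm, an assumed effect and equal correlation between days; none comes from the documents. The change is cheap and worth making.

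**What to change.** 1. In section 2a, add one administration of the existing daily survey before the Study 2 allocation is revealed and before any practice. It can be a separate Day 0, or the Day 1 survey required to be completed before first practice. Name it the Study 2 craving baseline.
2. In the Analysis Plan, define the levels of Time for Study 2. Use this baseline as covariate or reference in the craving analysis, and include Study 1 condition as a factor because the baseline still follows that manipulation.
3. Reconcile sections 2a and 8m on the duration of practice, and state on which survey days it falls.

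Moving the first saliva set to the baseline day is optional.

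Cost: with a Day 0, one more day and one more 5-minute survey per participant. Section 8k's total of $120 implies $5 per survey (30 + 14 × 5 + 3 × 5 + 5 = 120), so the added payment would be $5 each. Using Day 1 before practice adds neither a day nor a payment. Either way, the allocation must be withheld until the survey is submitted.
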